4.1 Primary Endpoint

4.1.1 Primary Safety Endpoint

The primary safety endpoint is the rate of device and/or procedure-related serious adverse events with onset within 7-days of any ablation procedure that uses the TactiCath SE catheter (initial or repeat procedure performed ≤ 180 days of initial procedure) that are defined below:

- Atrioesophageal fistula¹
- Cardiac tamponade/perforation¹
- Death
- Heart block
- Myocardial infarction (MI)
- Pericarditis²
- Phrenic nerve injury resulting in diaphragmatic paralysis
- Pneumothorax
- Pulmonary edema (respiratory insufficiency)
- Pulmonary vein stenosis¹
- Stroke/cerebrovascular accident (CVA)
- Thromboembolism
- Transient ischemic attack
- Vascular access complications (including major bleeding events³)

-
1. Atrioesophageal fistula, cardiac tamponade/perforation and pulmonary vein stenosis will be evaluated through 15-months.
 2. Pericarditis is a common occurrence for almost all procedures and will only be considered a primary safety endpoint event if the pericarditis pleuritic symptoms last longer than 7-days and/or requires hospitalization of greater than 24 hours for reasons other than for observational purposes only.
 3. Bleeding is a major complication of AF ablation if it requires and/or is treated with transfusion or results in a 20% or greater fall in hematocrit.

Definitions regarding the primary safety events are provided in **Appendix III**.

Serious AF/atrial flutter (AFL)/atrial tachycardia (AT) recurrences without coexisting conditions (e.g. thromboembolism, worsening heart failure, etc.) will be counted as effectiveness failures but will not count against the primary safety endpoint.

The performance goal is set at [REDACTED] as determined by relevant studies for persistent AF that utilize radiofrequency ablation. Refer to the Statistical Analysis Plan for details regarding the rationale for the performance goal.

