4.1.2 Primary Effectiveness Endpoint

The primary effectiveness endpoint for this clinical trial is freedom from AF/AFL/AT episodes of >30 seconds duration that is documented by an ECG (12-lead or TTM) or 24-hour Holter after the initial catheter ablation procedure through 15-months of follow-up (includes a 90-day blanking period followed by a 90-day therapy consolidation period). AF/AFL/AT recurrence during the blanking or therapy consolidation periods will not be considered a treatment failure. One repeat procedure is allowed for ablation of AF/AFL/AT recurrence during the blanking or therapy consolidation periods (≤ 180 days post-initial procedure) without being considered a treatment failure.

AF/AFL/AT recurrence will only be assessed by 12-lead ECG, TTM, and 24-hour Holter monitoring devices for assessment of this primary endpoint so that all subjects are monitored equally with devices of the same sensitivity and specificity. Collected ECG, TTM, and 24-hour Holter data from sites will be evaluated by a physician at a core laboratory for independent and unbiased assessment of AF recurrence for endpoint analysis.

There are multiple situations in which subjects will be considered primary effectiveness endpoint failures:

- If AF/AFL/AT recurrence (>30 second episode) occurs at any time after the therapy consolidation period (>180 days after the initial procedure), or
- If the subject requires a repeat procedure for the treatment of AF after the therapy consolidation period, the subject will be considered an effectiveness endpoint failure regardless of documentation of a >30 second AF/AFL/AT episode, or
- If the subject requires a second repeat procedure at any time after the initial procedure, or
- If the subject requires a new AAD or a previously failed AAD at a dose greater than the highest ineffective historical dose for AF after the therapy consolidation period, or
- If the subject requires a cardioversion (electrical or pharmacological) for the treatment of AF after the therapy consolidation period, or
- If the subject has a continuous atrial arrhythmia throughout a 12-lead ECG recording after the therapy consolidation period indicating arrhythmia recurrence, this will be considered sufficient documentation of recurrence unless there is evidence that the recorded arrhythmia is short-lived and less than 30 seconds.

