6.5 Blanking and Therapy Consolidation Periods

A blanking period of 90-days will be employed after the initial ablation procedure, followed by a 90-day therapy consolidation period and then a 9-month evaluation period for a total of 15-months of follow-up. Early recurrence of AF, AFL, or AT within the blanking period or therapy consolidation period will not be considered treatment failures. During the blanking and therapy consolidation periods, adjustment of antiarrhythmic medications, cardioversions, and one repeat ablation procedure may be performed.

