6.6.1 Repeat Ablation Procedures

One ablation procedure is allowed during the blanking and therapy consolidation periods (within 180 days post-initial procedure) due to AF/AFL/AT recurrence without being considered an effectiveness endpoint failure. The repeat procedure must be performed with the TactiCath SE catheter using the recommended parameters listed in the *Instructions for Use* document and in **Section 6.3**. The TactiCath SE catheter should not be used for repeat procedures that occur ≥ 181 days after the initial procedure or if the subject requires a third ablation procedure at any time during the follow-up period.

Certain assessments need to be performed if a repeat ablation is required. Neurological assessment and administration of the NIHSS by a certified assessor must be performed within 14-days of the repeat ablation procedure. Thrombus assessment must be performed as outlined in **Section 6.2.6** prior to ablating the subject. Verification of the exclusion of pericardial effusion by ICE or TTE must also be performed prior to the conclusion of the procedure.

A 7-day (± 2 days) follow-up phone call to the subject will need to be conducted after the repeat procedure. All other follow-up visits will occur as previously scheduled from the initial ablation procedure. Note that the 90-day blanking period followed by a 90-day therapy consolidation period are still in place from the initial procedure.

If AF/AFL/AT recurrence (>30 second episode) occurs at any time after this second ablation procedure or after the therapy consolidation period (≥ 181 days post-initial procedure), the subject will be considered an effectiveness endpoint failure. If the subject requires a repeat procedure for AF/AFL/AT recurrence after the therapy consolidation period or the subject requires a third ablation procedure, then the subject will be considered an effectiveness endpoint failure regardless of documentation of a >30 second AF/AFL/AT episode.

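### The safety section counts isolated serious AF/AFL/AT recurrences as effectiveness failures without a time limit, which conflicts as written with the effectiveness endpoint's exemption for recurrence through day 180

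*Protocol*

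**What the plan says.** Two rules bear on the same event.

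- **Safety section.** Protocol 4.1.1 addresses "Serious AF/atrial flutter (AFL)/atrial tachycardia (AT) recurrences without coexisting conditions" and says that they "will be counted as effectiveness failures but will not count against the primary safety endpoint". No window is attached, and the sentence does not refer to 4.1.2. The same sentence stands in Protocol Appendix IV and SAP 1.4.1. The endpoint it belongs to concerns "serious adverse events with onset within 7-days of any ablation procedure that uses the TactiCath SE catheter", where the procedure is the initial one or a repeat by day 180.
- **Effectiveness section.** Protocol 4.1.2 says "AF/AFL/AT recurrence during the blanking or therapy consolidation periods will not be considered a treatment failure". SAP 1.4.2 and Appendix IV carry the same exemption, and Protocol 6.5 restates it: "Early recurrence of AF, AFL, or AT within the blanking period or therapy consolidation period will not be considered treatment failures". In the list of failure situations, recurrence is a failure if it "occurs at any time after the therapy consolidation period (>180 days after the initial procedure". Follow-up "includes a 90-day blanking period followed by a 90-day therapy consolidation period", so the exempt period is 90 + 90 = 180 days. None of these places makes an exception for serious recurrence.

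No visible text in either document says which rule governs.

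**The concern.** The two rules decide who is a primary effectiveness failure, and the trial is single-arm and judged against a fixed performance goal. Take a subject readmitted with isolated AF on day 5, cardioverted as Protocol 6.5 permits, and free of arrhythmia afterwards. Inpatient hospitalization is one of the seriousness criteria in Protocol 7.1.2, so this can be a serious recurrence. Under the literal words of 4.1.1 the subject is an effectiveness failure; under 4.1.2 the subject is not.

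The SAP does not settle the matter, because it holds both rules itself (1.4.1 and 1.4.2). If the point stays open, the choice between a lower and a higher success rate could be made after the data are known.

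**Working it through.** The plan states no figure on this point, so the check compares texts first and then sizes the effect.

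**Step 1. Do the rules overlap?** The 4.1.1 sentence can be read in two scopes.
- Whole follow-up: the conflict covers every isolated serious recurrence from day 0 to day 180. After day 180 both rules generally call a recurrence a failure.
- The endpoint's own 7-day window: after the initial procedure this is days 0 to 7, wholly inside the exempt 180 days. After a repeat on day 180 it ends on day 180 + 7 = 187, so at most 7 days of any window fall outside. Nearly every recurrence covered is then one that 4.1.2 exempts.

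The rules conflict under either scope.

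**Step 2. Effect per subject.** Each subject whose only failure is an isolated serious recurrence by day 180 moves the success proportion by 1/N.
- N = 224 (planned enrolment): 1/224 = 0.45 points.
- N = 179: 1/179 = 0.56 points. The unredacted sample-size fragment in Protocol Section 8 gives 224 with 20% attrition, and 224 × 0.80 = 179.2. Using 179 as the effectiveness denominator is an assumption, because the analysis populations are redacted.

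**Step 3. Number of subjects.** The documents give no rate, so the following are assumptions: a share q of subjects has an isolated serious recurrence by day 180, and a share r of those would fail later under 4.1.2 anyway. Subjects in r are failures under both rules and must be left out. The net shift is q × (1 − r), and the number of subjects is 224 × q × (1 − r).

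| Assumed q | Assumed r | Subjects with the event | Subjects whose status changes | Shift in success |
|---|---|---|---|---|
| 3% | 60% | 6.7 | 6.7 × 0.40 = 2.7 | 1.2 points |
| 10% | 40% | 22.4 | 22.4 × 0.60 = 13.4 | 6.0 points |
| 1% (7-day window only) | 60% to 40% | 2.2 | 0.9 to 1.3 | 0.4 to 0.6 points |

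The literal 4.1.1 rule gives the lower success rate. The effectiveness hypothesis is redacted, so the distance from the goal cannot be judged.

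**Step 4. Could the affected set be smaller?** Yes. Protocol 7.3.1 and SAP 3.2 make recurrence a reportable adverse event only if it is significantly worse than the subject's baseline condition. Baseline here is persistent AF, documented as continuous. Fewer recurrences may therefore be recorded as serious events than the upper assumptions imply.

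**The case against.** The strongest reply is that the sentence only allocates. Recurrence is not among the 14 listed safety events, and the sentence says which endpoint it belongs to. Protocol 7.3.1 and SAP 3.2 use similar untimed shorthand when they say that recurrence affects the effectiveness endpoint. The section that defines effectiveness failure lists six situations, none of which is a serious recurrence before day 180, and adds an express exemption. Protocol 6.5 also allows medication changes, cardioversion and one repeat ablation in that period. This is the more natural reading of the intent, and it lowers the severity. It remains an inference: neither document states it, and the literal clause still gives a different answer.

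A reader might go further and infer that the analysis will score such subjects both ways, or will fail them. The documents do not support that. Recurrence for the endpoint is assessed from core-laboratory review of ECG, TTM and Holter data, while adverse events go to the events committee. No visible step turns the seriousness of an adverse event into an effectiveness failure. The analysis text in Protocol 8.2.1.2 and SAP 2.3.1.2 is blacked out and may hold the operating rule. If it does, the visible definitions would still need to be aligned with it.

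Nor does the clause reach every serious recurrence. It is limited to those without coexisting conditions.

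**Conclusion.** The point stands as a wording error in a primary endpoint rule, present in both documents. By day 180, an isolated serious recurrence has two stated classifications and no stated precedence.

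The firm figure is 0.45 points of primary success per affected subject at N = 224, or 0.56 at 179. Everything beyond that rests on assumed rates: about 3 to 13 subjects and 1.2 to 6.0 points across the whole 180 days, possibly fewer given the reporting rule, and about one subject for the 7-day window. A reader might take all 7 to 22 subjects with an early event (6.7 to 22.4 before rounding) as reclassified. That would be wrong, because those who fail later are failures under both rules.

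The severity is minor to moderate. The documents do not support treating this as a must-fix flaw: the likely intent is clear, and no visible analysis step applies the literal clause.

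**What to change.** In Protocol 4.1.1, Protocol Appendix IV and SAP 1.4.1, keep the statement that these recurrences do not count as safety events. Replace the effectiveness half of the clause with: *they are counted as effectiveness failures only if they meet the primary effectiveness failure criteria*. Cite Section 4.1.2 in the two Protocol places and Section 1.4.2 in the SAP.

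Do not add a limit such as more than 180 days after the initial procedure. It would misstate the definition, in which a second repeat procedure is a failure at any time. A bare pointer carries the whole definition across.

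Separately, reconcile these passages with Protocol 6.6.1. It begins "If AF/AFL/AT recurrence (>30 second episode) occurs at any time after this second ablation procedure or after the therapy consolidation period" and makes such a recurrence a failure, so after a repeat ablation it also counts recurrence before day 181. That is a different conflict with the 4.1.2 exemption and needs its own decision; the new clause should not settle it by side effect.

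The cost is one clause in three places, with no change to data collection, visits or patient burden. If the redacted analysis text already states the rule, the new clause should be checked against it.

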4.1.1.1 Rationale for Selection of the Primary Safety Endpoint

[REDACTED]

[REDACTED]

occur within the first 7-days following an ablation procedure. It has become industry standard to report

[REDACTED]

[REDACTED]

[REDACTED]

[REDACTED]

[REDACTED]

[REDACTED]	[REDACTED]	[REDACTED]	[REDACTED]
[REDACTED]	[REDACTED]	[REDACTED]	[REDACTED]
[REDACTED]	[REDACTED]	[REDACTED]	[REDACTED]
[REDACTED]	[REDACTED]	[REDACTED]	[REDACTED]
[REDACTED]	[REDACTED]	[REDACTED]	[REDACTED]
[REDACTED]	[REDACTED]	[REDACTED]	[REDACTED]
[REDACTED]	[REDACTED]	[REDACTED]	[REDACTED]
[REDACTED]	[REDACTED]	[REDACTED]	[REDACTED]

[REDACTED]

[REDACTED]	[REDACTED]	[REDACTED]	[REDACTED]
[REDACTED]	[REDACTED]	[REDACTED]	[REDACTED]
[REDACTED]	[REDACTED]	[REDACTED]	[REDACTED]
[REDACTED]	[REDACTED]	[REDACTED]	[REDACTED]

4.1.2 Primary Effectiveness Endpoint

The primary effectiveness endpoint for this clinical trial is freedom from AF/AFL/AT episodes of >30 seconds duration that is documented by an ECG (12-lead or TTM) or 24-hour Holter after the initial catheter ablation procedure through 15-months of follow-up (includes a 90-day blanking period followed by a 90-day therapy consolidation period). AF/AFL/AT recurrence during the blanking or therapy consolidation periods will not be considered a treatment failure. One repeat procedure is allowed for ablation of AF/AFL/AT recurrence during the blanking or therapy consolidation periods (≤ 180 days post-initial procedure) without being considered a treatment failure.

AF/AFL/AT recurrence will only be assessed by 12-lead ECG, TTM, and 24-hour Holter monitoring devices for assessment of this primary endpoint so that all subjects are monitored equally with devices of the same sensitivity and specificity. Collected ECG, TTM, and 24-hour Holter data from sites will be evaluated by a physician at a core laboratory for independent and unbiased assessment of AF recurrence for endpoint analysis.

There are multiple situations in which subjects will be considered primary effectiveness endpoint failures:

- If AF/AFL/AT recurrence (>30 second episode) occurs at any time after the therapy consolidation period (>180 days after the initial procedure), or
- If the subject requires a repeat procedure for the treatment of AF after the therapy consolidation period, the subject will be considered an effectiveness endpoint failure regardless of documentation of a >30 second AF/AFL/AT episode, or
- If the subject requires a second repeat procedure at any time after the initial procedure, or
- If the subject requires a new AAD or a previously failed AAD at a dose greater than the highest ineffective historical dose for AF after the therapy consolidation period, or
- If the subject requires a cardioversion (electrical or pharmacological) for the treatment of AF after the therapy consolidation period, or
- If the subject has a continuous atrial arrhythmia throughout a 12-lead ECG recording after the therapy consolidation period indicating arrhythmia recurrence, this will be considered sufficient documentation of recurrence unless there is evidence that the recorded arrhythmia is short-lived and less than 30 seconds.

As cavotricuspid isthmus-dependent atrial flutter is easily treated with cavotricuspid isthmus ablation and is not an iatrogenic arrhythmia following a left atrial ablation procedure for AF, occurrence of cavotricuspid isthmus-dependent atrial flutter confirmed by entrainment maneuvers that occurs at any time during the follow-up period and is ablated, will not be considered a primary effectiveness endpoint failure.

[figure not shown]
[figure not shown]
[figure not shown]

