3.2 Measures Taken to Avoid and Minimize Bias

Multiple measures will be taken to avoid and minimize bias in this clinical investigation. First, PERSIST-END is a prospective clinical investigation in which the outcome is unknown at the time of enrollment and

all subjects must meet the defined eligibility criteria to minimize selection bias. Next, guidance will be provided to sites regarding data collection for questionnaires and the post-procedure follow-up phone calls to be performed at 7-days, 6-months, and 12-months post-procedure. Additionally, case report forms for data collection will be provided to sites, which will minimize inter-observer variability.

Evaluation of primary endpoint data will be performed by an independent core laboratory and Clinical Events Committee (CEC). Collected electrocardiogram (ECG), trans-telephonic monitoring (TTM) data, and 24-hour Holter data from sites will be evaluated by a physician at a core laboratory to determine AF recurrence for subjects. Adverse events will be adjudicated by a CEC made up of physicians who are not investigators in the trial. Although the investigators at each site will perform their own adjudication regarding outcome data, only the core lab and the CEC's adjudication of the collected data will be used for analysis in order to minimize bias.

Protocols are also in place to minimize lost to follow-up subjects and for handling missing data. Sensitivity analyses will be performed demonstrating the impact missing data may have on the trial.

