6.7 Core Laboratory

A core lab will be used for the collection, interpretation, and collation of data collected from the following sources:

- TTM
- 24-hour Holter monitoring
- 12-lead ECGs

The core lab will provide independent review of this data by appropriately trained personnel using standardized procedures to interpret TTM, 24-hour Holter, and 12-lead ECG tracings for adjudication of atrial arrhythmias. Findings will be communicated to the investigator and to Abbott. The core lab's adjudication findings will be used for analysis.

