## Statistical Analysis Plan

and is ablated, will not be considered a primary effectiveness endpoint failure.

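### The flutter exemption in the primary effectiveness endpoint has no named independent confirmer, can only favour success, and conflicts with the repeat-procedure rule in Protocol 6.6.1

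*Protocol*

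**What the plan says.** **The general rule.** Protocol 4.1.2 lists as a failure: "If AF/AFL/AT recurrence (>30 second episode) occurs at any time after the therapy consolidation period (>180 days after the initial procedure), or". The sources are restricted: "AF/AFL/AT recurrence will only be assessed by 12-lead ECG, TTM, and 24-hour Holter monitoring devices for assessment of this primary endpoint". A core laboratory physician reads them.

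**The exemption.** The same section then removes from the failures "cavotricuspid isthmus-dependent atrial flutter confirmed by entrainment maneuvers that occurs at any time during the follow-up period and is ablated". SAP 1.4.2 repeats it; such flutter, if entrainment-confirmed "and is ablated, will not be considered a primary effectiveness endpoint failure". Neither document says who confirms the entrainment finding.

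**Who adjudicates.** Protocol 3.2 notes that site investigators make their own judgement of outcomes, but says "only the core lab and the CEC's adjudication of the collected data will be used for analysis in order to minimize bias". Protocol 6.7 sets the core lab's task as "using standardized procedures to interpret TTM, 24-hour Holter, and 12-lead ECG tracings for adjudication of atrial arrhythmias". Protocol 3.2 assigns adverse events to the CEC. Protocol 10.7.2 speaks of pre-specified events under a charter, and the CEC definitions in Appendix III are all safety events. Protocol 6.3 sends the recorded procedure data to the sponsor.

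**Other classification text.** Protocol 6.6.1 makes a subject a failure if a repeat procedure is needed for AF, AFL or AT after the consolidation period, or if a third ablation is needed, whether or not an episode was documented. It has no exception for isthmus-dependent flutter. The endpoint text of the CIP summary (Appendix IV) does not mention the exemption.

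**The concern.** The plan's main protection against biased outcome assessment is that independent readers, not sites, decide the endpoint. The flutter exemption depends on something those readers are not said to receive. A Holter or ECG can show the core lab a flutter episode longer than 30 seconds, but entrainment is a pacing manoeuvre made during an invasive study and appears in none of the three sources the core lab reads.

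Where the exemption operates, it works in one direction only: it turns a failure into a non-failure. The trial has a single arm and is judged against a fixed performance goal, so there is no control arm in which the same error would occur and cancel. The operator necessarily knows the treatment given.

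A second problem is that the same subject can be a failure or a non-failure depending on which section the analyst follows.

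**Working it through.** **1. One subject, four pieces of text.** Take a subject whose Holter on day 240 shows flutter longer than 30 seconds. It is found at a second procedure to be isthmus-dependent by entrainment, and is ablated.

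| Text | Classification |
|---|---|
| Protocol 4.1.2, recurrence after day 180 | Failure |
| Protocol 4.1.2 and SAP 1.4.2, flutter exemption | Not a failure |
| Protocol 6.6.1, repeat procedure for AFL after consolidation | Failure |
| Appendix IV, recurrence after day 180, no exemption given | Failure |

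The repeat-procedure item in 4.1.2 refers only to treatment of AF, so it does not settle the case. The wording in 6.6.1 includes AFL and does reach it. Recurrence up to day 180 is not a failure in any event, so for recurrence the exemption matters only later, which is where 6.6.1 opposes it.

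**2. Who could confirm it.** Core lab: TTM, Holter and 12-lead ECG only (6.7). CEC: adverse events (3.2), pre-specified events under a charter (10.7.2), safety definitions (Appendix III). Sponsor: receives procedure data (6.3), but no confirming role is described. The operator is what remains. That is an inference; no sentence says so.

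**3. Number of subjects.** The one legible sample size line (Protocol 8.3, tied to the 16.8% safety goal) gives 224 with 20% attrition. Working back: 224 × (1 − 0.20) = 179.2, and 179 / 0.80 = 223.75, which rounds up to 224. So 224 corresponds to 179 evaluable subjects. Alpha, power and the expected rate are blacked out, so the power calculation cannot be reproduced.

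**4. Shift per exempted subject.** 1/224 = 0.45 points; 1/179 = 0.56 points. Four subjects: 4/224 = 1.8 points; 4/179 = 2.2 points.

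**5. False-pass chance (illustration).** Assumptions:
- Goal of 40%. The primary goal is blacked out; 40% is the visible single-procedure secondary goal in Appendix IV.
- n = 179 and an exact one-sided test at 0.025.
- True success rate exactly at the goal.
- A share d of all subjects wrongly exempted.

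The smallest r with P(X ≥ r | 179, 0.40) ≤ 0.025 is r = 86, where the probability is 0.018. The false-pass chance is then P(X ≥ 86 | 179, 0.40 + d):

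| d | Chance |
|---|---|
| 0 | 1.8% |
| 1% (about 2 subjects) | 3.3% |
| 2% (about 4 subjects) | 6.0% |

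The choice of 40% does not drive this. Over goals of 35%, 40%, 45% and 50% and n of 179 or 224, the 2% case gives 5.9% to 8.6%.

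**6. A result near the line.** If 82 of 179 succeed and four exemptions bring the count to 86, the one-sided p-value is 0.018 with them and 0.066 without.

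**The case against.** The strongest reply is that silence is not contradiction. The exemption does not say who confirms entrainment, and Protocol 3.2 can be read as governing it, so that an investigator's claim alone would not decide the endpoint. The natural places for a review step cannot be seen: the CEC charter is not supplied, its remit in 10.7.2 is not worded as adverse events only, and the analysis text in SAP 2.3.1.2 is almost wholly blacked out. This stands. A reader might infer that the plan lets an unblinded operator overturn a core lab reading, in breach of 3.2. The documents do not support that; they show an unassigned step.

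A reader might also infer that no sensitivity analysis covers the exemption. What can be said is that the SAP contents list three headings under 2.13 (missing data, protocol compliance, Covid-19) and none names it; the text beneath is largely not legible.

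The exemption is also narrow. Isthmus dependence, entrainment confirmation and ablation are all needed, and a separate AF, AT or other flutter recurrence is not excused. Protocol 6.3 requires flutter ablation with verified block at the index procedure for subjects with a history of typical flutter or with induced isthmus-dependent flutter, which should limit later cases. And if 6.6.1 prevails, the exemption may have little effect after day 180. These points bear on size. They do not say who confirms the finding, and the last is itself the conflict to be resolved.

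Finally, 6.6.1 says the study catheter should not be used for repeats from day 181, so study recordings of exactly these procedures are not assured. That is a real cost of requiring confirmation, and a reason to state the requirement in advance.

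**Conclusion.** The point holds in this form. On the legible text, no independent body is assigned the finding on which the flutter exemption depends, the exemption can only favour success where it operates, and it conflicts with Protocol 6.6.1 and is missing from the CIP summary. That the operator is the source is an inference, and a review step may exist in text that cannot be seen.

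The shift of 0.45 to 0.56 points per subject is arithmetic. The rise in false-pass chance from 1.8% to between 3.3% and 6.0% rests on an assumed goal, alpha, test, sample size and rate of wrong exemption, and gives scale only. Wrong exemption of 5% of subjects would give 22.8% on the same assumptions, but nothing in the documents suggests a rate that high, and it should carry no weight. The documents give neither a flutter rate nor an exemption rate.

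The clinical reason for the exemption is not disputed. The change is worth making because it is cheap and protects the primary result from a question that would be hard to answer afterwards.

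**What to change.** 1. In SAP 2.13, pre-specify a sensitivity analysis of the primary effectiveness endpoint that counts every subject exempted under the flutter rule as a failure, and report the number exempted.
2. In Protocol 4.1.2 and 6.7 and SAP 1.4.2, state that the exemption counts in the primary analysis only when the existing core lab or CEC confirms it from retained procedure tracings. If the CEC charter already provides this, cite the section instead.
3. Reconcile Protocol 4.1.2, 6.6.1 and Appendix IV so that each such subject has one classification.

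The cost is one additional analysis, a modest widening of what an existing body reviews (intracardiac recordings are outside the core lab's present scope), and a request to sites to keep the tracings. The downside is that a valid exemption may be lost where tracings were not kept. No treatment or eligibility rule needs to change.
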